### 6.3.4 Follow-up for toxicities

Participants whose treatment is interrupted or permanently discontinued due to an adverse event or clinically significant laboratory value, must be followed up at least once a week (or more frequently if required by institutional practices, or if clinically indicated) for 4 weeks, and subsequently at approximately 4-week intervals, until resolution or stabilization of the event, whichever comes first. Appropriate clinical experts should be consulted as deemed necessary. All participants must be followed up for adverse events and serious adverse events for 30 days following the last doses of nazartinib and capmatinib.

An unscheduled assessment should be performed in all cases below where toxicity monitoring is recommended more frequently than defined by the schedule of assessments. Subsequent monitoring must be performed as per the regular visit schedule.

**Table 6-16 Toxicity follow-up evaluation**

TOXICITY	FOLLOW-UP EVALUATION
HEMATOLOGICAL	
Febrile neutropenia, Neutropenia ≥ CTCAE grade 3 Thrombocytopenia ≥ CTCAE grade 3 Anemia ≥ CTCAE grade 3	Test weekly (or more frequently if clinically indicated) until ≤ CTCAE grade 2. Perform physical exam for check on bruising in case of major thrombocytopenia.
RENAL	
Serum creatinine ≥ CTCAE grade 2	Test weekly (or more frequently if clinically indicated) until ≤ CTCAE grade 1 or baseline. Participants will be instructed to increase hydration until resolution to ≤ CTCAE grade 1 or baseline.
HEPATIC	
Isolated total bilirubin elevation	Total bilirubin CTCAE Grade 1: Monitor LFTs per protocol or more frequently if clinically indicated Total bilirubin CTCAE Grade 2: Weekly monitoring of LFTs, or more frequently if clinically indicated, until resolved to ≤ 1.5 x ULN Total bilirubin CTCAE Grade 3: Weekly monitoring of LFTs, or more frequently if clinically indicated, until resolved to ≤ 1.5 x ULN. If resolved in > 7 days, after discontinuing the participant from capmatinib permanently, the participant should be monitored weekly (including LFTs), or more frequently if clinically indicated, until total bilirubin have resolved to baseline or stabilization over 4 weeks Total bilirubin CTCAE Grade 4: After discontinuing the participant from capmatinib permanently, the participant should be monitored weekly (including LFTs), or more frequently if clinically indicated, until total bilirubin have resolved to baseline or stabilization over 4 weeks
Isolated AST/ALT elevation	AST/ALT CTCAE Grade 2 elevation: For participants with baseline value ≤ 3.0 x ULN: repeat LFTs as soon as possible, preferably within 48-72 hr from awareness of the abnormal results; if abnormal lab values are confirmed upon the repeat test, then monitor LFTs weekly, or more frequently if clinically indicated, until resolved to ≤ 3.0 x ULN. For participants with baseline value > 3.0 x ULN: monitor LFTs per protocol or more frequently if clinically indicated AST/ALT CTCAE Grade 3 elevation: For AST/ALT elevation > 5.0 - 10.0 x ULN: For participants with baseline value ≤ 3.0 x ULN: repeat LFTs as soon as possible, preferably within 48-72 hr from awareness of the abnormal results; monitor LFTs weekly, or more frequently if clinically indicated, until resolved to ≤ 3.0 x ULN. For participants with baseline value > 3.0 x ULN: repeat LFTs as soon as possible, preferably within 48-72 hr from awareness of the abnormal results; if abnormal lab values are confirmed upon the repeat test, then monitor LFTs, weekly, or more frequently if clinically indicated, until resolved to ≤ 5.0 x ULN. For AST/ALT elevation > 10.0 - 20.0 x ULN: Repeat LFTs as soon as possible, preferably within 48-72 hr from awareness of the abnormal results; monitor LFTs weekly, or more frequently if clinically indicated, until resolved to ≤ baseline. AST/ALT CTCAE Grade 4 elevation:

TOXICITY	FOLLOW-UP EVALUATION
	Repeat LFTs as soon as possible, preferably within 48-72 hr from awareness of the abnormal results; monitor LFTs weekly, or more frequently if clinically indicated, until resolved to baseline or stabilization over 4 weeks.
Combined elevations in ALT and/or AST with concurrent total bilirubin increase, in the absence of cholestasis or hemolysis	
Combined elevations of AST or ALT and total bilirubin: After discontinuing the participant from capmatinib permanently, repeat LFTs as soon as possible, preferably within 48 hr from awareness of the abnormal results, then with weekly monitoring of LFTs, or more frequently if clinically indicated, until AST, ALT, or bilirubin have resolved to baseline or stabilization over 4 weeks.
 
Core LFTs consist of ALT, AST, GGT, total bilirubin (fractionated [direct and indirect], if total bilirubin > 2.0 x ULN), and alkaline phosphatase (fractionated [quantification of isoforms], if alkaline phosphatase > 2.0 x ULN).

METABOLIC	
amylase or lipase ≥ CTCAE grade 3	
Test weekly (or more frequently) until ≤ CTCAE grade 2.
 
A CT scan or equivalent imaging procedure to assess the pancreas, liver, and gallbladder is recommended within 7 days of the first occurrence of any ≥ CTCAE grade 3 result, to exclude disease progression or potential other liver or pancreatic disease.

CARDIAC	
≥ CTCAE grade 3	Test weekly (or more frequently) until ≤ CTCAE grade 2.
QTcF ≥ 501 ms (CTCAE grade 3)	
When QTcF ≥ 501 ms (CTCAE grade 3), perform the following: Call the study's central ECG review laboratory immediately and request an immediate manual read of the ECG. Perform an analysis of serum potassium, calcium, phosphorus, and magnesium, and if below lower limit of normal, correct with supplements to within normal limits. Review concomitant medication usage for the potential to prolong the QT-interval. Check compliance with correct dose and administration of capmatinib. Perform a repeat ECG within one hour of the first QTcF of ≥ 501 ms. If QTcF remains ≥ 501 ms, repeat ECG as clinically indicated, but at least once daily until the QTcF returns to < 501 ms. Repeat ECGs 7 days and 14 days (and then every 21 days) after dose resumption for all participants who had therapy interrupted due to QTcF ≥ 501 ms. If QTcF of ≥ 501 ms recurs, repeat ECGs as described above.
 
Notes: The investigator should contact the Novartis Medical Lead or designee regarding any questions that arise if a participant with QTcF prolongation should be maintained on study. If the central ECG report shows a QTcF ≥ 501 msec (not previously documented on the site machine), contact the participant and instruct him/her to suspend capmatinib and return for a repeat ECG as soon as possible. The central ECG reader should be called for a manual read of the repeat ECG immediately, and the above guidance followed.

GASTROINTESTINAL	
Diarrhea	Investigate potential concomitant medication, food or comorbidity driven causes of diarrhea (including infectious causes) and remedy these causes if possible (e.g., discontinuation of concomitant medication, dietary modification, treatment of comorbidity).

TOXICITY	FOLLOW-UP EVALUATION
	
The participant should be monitored for signs of dehydration and instructed to take preventive measures against dehydration as soon as diarrhea occurs. Antidiarrheal medication must be initiated at the first sign of abdominal cramping, loose stools or overt diarrhea. Concomitant medication for the treatment of diarrhea should follow local practice and the investigator's best judgment and may follow "the recommended guidelines for the treatment of cancer treatment-induced diarrhea" (Benson et al 2004). For example:
 
For uncomplicated diarrhea (grade 1 or 2 without complicating signs or symptoms), loperamide given at a standard dose (e.g. initial administration of 4 mg, then 2 mg every 2-4 hr, maximum of 16 mg/day), along with oral hydration and dietetic measures should be considered. Note: complicating signs or symptoms include moderate to severe cramping, decreased performance status, fever, neutropenia, frank bleeding or dehydration.
 
For complicated diarrhea (all grade 3 or 4, grade 1-2 with complicating signs or symptoms), management should involve intravenous (IV) fluids, and consider treatment with octreotide (at starting dose of 100 to 150 µg sub-cutaneous tid or 25 to 50 µg/h IV) and antibiotics (e.g., fluoroquinolone) should be given

Nausea and Vomiting	
The investigator should consider/investigate potential concomitant medication, food or comorbidity driven causes of nausea and/or vomiting and remedy these causes if possible (e.g., discontinuation of concomitant medication, dietary modification, treatment of comorbidity).
 
Individualized supportive and anti-emetic treatment should be initiated, as appropriate, at the first signs and/or symptoms of these AEs. In participants with vomiting, the participant should be monitored for signs of dehydration and instructed to take preventive measures against dehydration.
 
Concomitant medication for the treatment of nausea and/or vomiting should follow local practice and the investigator's best judgment.

SKIN TOXICITY	
Rash and Photosensitivity	
CTCAE grade 1	Consider to initiate institute appropriate skin toxicity therapy (such as antihistamines, topical corticosteroids and low-dose systemic corticosteroids)
CTCAE grade 2	Initiate/intensify appropriate skin toxicity therapy (such as antihistamines, topical corticosteroids and low-dose systemic corticosteroids)
≥ CTCAE grade 3	Intensify appropriate skin toxicity therapy and monitor weekly or more frequently until resolved to grade ≤ 1
Peripheral edema	
CTCAE grade ≤ 2	Consider to initiate conservative measures such as leg elevation, compression stockings, and dietary salt modification as clinically indicated
CTCAE grade ≥ 3	Initiate/intensify conservative measures
RESPIRATORY, THORACIC AND MEDIASTINAL DISORDERS	
ILD/Pneumonitis	
CTCAE Grade 1	
CT scan (high-resolution with lung windows) recommended, with serial imaging to monitor for resolution or progression- re-image at least every 3 weeks
 
Monitor for symptoms every 2-3 days - Clinical evaluation and laboratory work-up for infection

TOXICITY	FOLLOW-UP EVALUATION
	Monitoring of oxygenation via pulse oximetry recommended Consultation of pulmonologist recommended
CTCAE Grade 2	CT scan (high-resolution with lung windows) 
 
• Monitor symptoms daily, consider hospitalization
 
• Clinical evaluation and laboratory work up for infection
 
• Consult pulmonologist
 
• Pulmonary function tests a - if normal at baseline, repeat every 8 weeks
 
• Bronchoscopy with biopsy and/or Bronchoalveolar Lavage (BAL) recommended c
 
 Symptomatic therapy including corticosteroids if clinically indicated (1 to 2 mg/kg/day prednisone or equivalent as clinically indicated) b
CTCAE Grade 3 and Grade 4	CT scan (high-resolution with lung windows) Clinical evaluation and laboratory work-up for infection Consult pulmonologist Pulmonary function tests a - if < normal, repeat every 8 weeks until ≥ normal Bronchoscopy with biopsy and/or BAL if possible c Treat with i.v. steroids (methylprednisolone 125 mg) as indicated. When symptoms improve to ≤ Grade 1, a high dose oral steroid (prednisone 1 to 2 mg/kg once per day or dexamethasone 4 mg every 4 hr) b If i.v. steroids followed by high dose oral steroids does not reduce initial symptoms within 48 to 72 hours, consider non-corticosteroid immunosuppressive medication
a Pulmonary function tests (PFTs) to include: diffusing capacity of the lungs for carbon monoxide corrected for hemoglobin (DLCO); spirometry; resting oxygen saturation. Guideline for significant deterioration in lung function: a Decrease in spirometry and/or DLCO of 30% and/or O 2 saturation ≤ 88% at rest on room air. b Duration and dose of course of corticosteroids will vary according to circumstances but should be as limited as possible. Consider tapering dosage at end. c If bronchoscopy is performed, bronchoalveolar lavage (BAL) should be done where possible to exclude alveolar hemorrhage, opportunistic infections, cell count + determination lymphocyte CD4/8 count where possible.	

### 6.3.4.1 Follow up on potential QTcF prolongation

#### In case of QTcF >500 ms, (or QTcF prolongation >60 ms from baseline)

- Assess the quality of the ECG recording and the QT value and repeat if needed
- Interrupt study treatment (capmatinib + nazartinib)
- Determine the serum electrolyte levels (in particular hypokalemia, hypomagnesemia). If abnormal, correct abnormalities before resuming study drug treatment (capmatinib + nazartinib).
- Review concomitant medication use for other causes for QT prolongation, and for drugs with the potential to increase the risk of drug exposure related QT prolongation
- Check study drug dosing schedule and study treatment compliance
- Consider collecting a time-matched PK sample, and record time and date of last study drugs intake.
- Perform a repeat ECG within one hour of the first QTcF of >500 ms.

### **After confirming ECG reading at site, if QTcF > 500 ms**

- Interrupt study treatment (capmatinib + nazartinib)
- Repeat ECG and confirm ECG diagnosis by a cardiologist or central ECG lab
- If QTcF confirmed > 500 ms:
  - Correct electrolytes, eliminate culprit concomitant treatments, and identify clinical conditions that could potentially prolong the QT
  - Consult with a cardiologist (or qualified specialist)
  - Increase cardiac monitoring as clinically indicated, until the QTcF returns to  $\leq 480$  ms.
  - Repeat ECGs 7 days and 14 days (and then every 21 days) after dose resumption for all participants who had therapy interrupted due to QTcF > 500 ms.
- After resolution to  $\leq 480$  ms, consider re-introducing study treatment (capmatinib + nazartinib) at reduced dose, and increase ECG monitoring:
  - If QTcF remains  $\leq 500$  ms after dose reduction, continue planned ECG monitoring during subsequent study treatment
  - If QTcF recurs > 500 ms after dose reduction, discontinue participant from trial.

#### **6.3.4.2 Follow up on potential drug-induced liver injury (DILI) cases**

Participants with transaminase increase combined with total bilirubin increase may be indicative of potential DILI, these cases should be considered as clinically important events and assessed appropriately to establish the diagnosis. The required clinical information, as detailed below, should be sought to obtain the medical diagnosis of the most likely cause of the observed laboratory abnormalities.

The threshold for potential DILI may depend on the participant's baseline AST/ALT and total bilirubin value; participants meeting any of the following criteria will require further follow-up as outlined below:

- For participants with normal ALT and AST and total bilirubin value at baseline: AST or ALT > 3.0 x ULN combined with total bilirubin > 2.0 x ULN
- For participants with elevated AST or ALT or total bilirubin value at baseline: [AST or ALT > 3 x baseline] OR [AST or ALT > 8.0 x ULN], whichever is lower, combined with [total bilirubin > 2 x baseline AND > 2.0 x ULN]

As DILI is essentially a diagnosis of exclusion, other causes of abnormal liver tests should be considered and their role clarified before DILI is assumed as the cause of liver injury.

- Laboratory tests should include ALT, AST, albumin, creatine kinase, total bilirubin, direct and indirect bilirubin, GGT, Glutamate dehydrogenase (GLDH), prothrombin time (PT)/INR and alkaline phosphatase.
- A detailed history, including relevant information, such as review of ethanol, concomitant medications, herbal remedies, supplement consumption, history of any pre-existing liver conditions or risk factors, should be collected.
- Evaluate status of liver metastases (new or exacerbation) or vascular occlusion – e.g., using CT, MRI, or duplex sonography.

- Perform relevant examinations (Ultrasound or MRI, Endoscopic retrograde cholangiopancreatography (ERCP)) as appropriate, to rule out an extrahepatic cause of cholestasis. Cholestasis (is defined as an ALP elevation > 2.0 x ULN with R value < 2 in participants without bone metastases, or elevation of the liver-specific ALP isoenzyme in participants with bone metastases).
- Note: The R value is calculated by dividing the ALT by the ALP, using multiples of the ULN for both values. It denotes whether the relative pattern of ALT and/or ALP elevation is due to cholestatic ( $R \leq 2$ ), hepatocellular ( $R \geq 5$ ), or mixed ( $R > 2$  and  $< 5$ ) liver injury. In clinical situations where it is suspected that ALP elevations are from an extrahepatic source, the GGT can be used if available. GGT may be less specific than ALP as a marker of cholestatic injury, since GGT can also be elevated by enzyme induction or by ethanol consumption. It is more sensitive than ALP for detecting bile duct injury.
- [Table 6-17](#) provides guidance on specific clinical and diagnostic assessments which can be performed to rule out possible alternative causes of observed LFT abnormalities. Guidance on specific clinical and diagnostic assessments which can be performed to rule out possible alternative causes of observed LFT abnormalities.

**Table 6-17 Guidance to rule out other alternative causes of observed LFT abnormalities**

Disease	Assesment
Hepatitis A, B, C, E	IgM anti-HAV; HBsAg, IgM & IgG anti-HBc, HBV DNA; anti-HCV, HCV RNA, IgM & IgG anti-HEV, HEV RNA
Cytomegalovirus (CMV), Herpes Simplex Virus (HSV), Epstein-Barr Virus (EBV) infection	IgM & IgG anti-CMV, IgM & IgG anti-HSV; IgM & IgG anti-EBV
Autoimmune hepatitis	Antinuclear Antibodies (ANA) & Anti-Smooth Muscle Antibody (ASMA) titers, total IgM, IgG, IgE, IgA
Alcoholic hepatitis	Ethanol history, GGT, Mean Corpuscular Volume (MCV), CD-transferrin
Nonalcoholic steatohepatitis	Ultrasound or MRI
Hypoxic/ischemic hepatopathy	Medical history: acute or chronic congestive heart failure, hypotension, hypoxia, hepatic venous occlusion. Ultrasound or MRI.
Biliary tract disease	Ultrasound or MRI, ERCP as appropriate.
Wilson disease (if <40 yrs old)	Caeruloplasmin
Hemochromatosis	Ferritin, transferrin
Alpha-1-antitrypsin deficiency	Alpha-1-antitrypsin

- Obtain PK sample, as close as possible to last dose of study drug, to determine exposure to study treatment and metabolites.
- Following appropriate causality assessments, as outlined above, the causality of the treatment is estimated as “probable” i.e., >50% likely, if it appears greater than all other possible causes of liver injury combined. The term “treatment-induced” indicates *probably caused* by the treatment, not by something else, and only such a case can be considered a DILI case and should be reported as an SAE.

All cases confirmed on repeat testing meeting the laboratory criteria defined above, with no other alternative cause for LFT abnormalities identified should be considered as “medically

significant”, thus, met the definition of SAE (Section 8.2.1) and reported as SAE using the term “potential drug-induced liver injury”. All events should be followed up with the outcome clearly documented.

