## 8.2 Serious adverse events

### 8.2.1 Definitions

Serious adverse event (SAE) is defined as one of the following:

- Is fatal or life-threatening
- Results in persistent or significant disability/incapacity
- Constitutes a congenital anomaly/birth defect
- Is medically significant, i.e., defined as an event that jeopardizes the participant or may require medical or surgical intervention to prevent one of the outcomes listed above
- Requires inpatient hospitalization or prolongation of existing hospitalization,

Note that hospitalizations for the following reasons should not be reported as serious adverse events:

- Routine treatment or monitoring of the studied indication, not associated with any deterioration in condition
- Elective or pre-planned treatment for a pre-existing condition that is unrelated to the indication under study and has not worsened since signing the informed consent

- Social reasons and respite care in the absence of any deterioration in the participant's general condition

Note that treatment on an emergency outpatient basis that does not result in hospital admission and involves an event not fulfilling any of the definitions of a SAE given above is not a serious adverse event

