### 8.2.2 SAE Reporting

For participants with unknown EGFR and/or MET statuses and who sign the molecular pre-screening ICF, SAE collection will start upon signing the molecular pre-screening ICF. SAEs will only be reported if the event is suspected to be causally related to a study procedure as assessed by the investigator (e.g. an invasive procedure such as biopsy). SAEs will be followed until resolution or until clinically relevant improvement or stabilization. If the main ICF is not signed (molecular screen failure), SAE collection ends 30 days after the last study related procedure.

Serious adverse events considered by the investigator to be possibly related to a biopsy procedure will be indicated as such in the AE eCRF. This information will be followed-up for 30 days after the biopsy procedure.

For participants with known EGFR and/or MET statuses who sign the main study ICF, SAE collection starts at time of main study informed consent whether the participant is a screen failure or not.

To ensure participant safety, every SAE, regardless of causality, occurring after the participant has provided informed consent and until 30 days after the participant has stopped study treatment must be reported to Novartis safety immediately, without undue delay, but under no circumstances later than within 24 hours of obtaining knowledge of the events (Note: if more stringent, local regulations regarding reporting timelines prevail).

Any SAEs experienced after this 30 days period (or 5 half-lives, whichever is longer) should only be reported to Novartis safety if the investigator suspects a causal relationship to the study treatment, unless otherwise specified by local law/regulations. Recurrent episodes, complications, or progression of the initial SAE must be reported as follow-up to the original episode immediately, without undue delay, but under no circumstances later than within 24 hours of the Investigator receiving the follow-up information (Note: if more stringent, local regulations regarding reporting timelines prevail). An SAE occurring at a different time interval or otherwise considered completely unrelated to a previously reported one should be reported separately as a new event.

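### Section 6.3.4.2 limits SAE reporting of liver events to cases judged more than 50% likely treatment-caused, while its next paragraph and Section 8.2 set no such limit

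*Protocol*

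**What the plan says.** Section 6.3.4.2 sets laboratory criteria for potential drug-induced liver injury (DILI) and a work-up to look for other explanations, supported by Table 6-17. Two statements on SAE reporting follow the table.

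- **The bullet.** After the work-up, causality is graded. It is probable, "i.e., >50% likely, if it appears greater than all other possible causes of liver injury combined". The bullet reserves the term treatment-induced for such cases and ends: "only such a case can be considered a DILI case and should be reported as an SAE".
- **The closing paragraph.** "All cases confirmed on repeat testing meeting the laboratory criteria defined above, with no other alternative cause for LFT abnormalities identified" are to be regarded as medically significant. The paragraph says that they "met the definition of SAE (Section 8.2.1) and reported as SAE using the term" potential drug-induced liver injury. It contains no probability threshold.

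Two general provisions also apply. Section 8.2.1 lists the SAE criteria, one of which reads: "Is medically significant, i.e., defined as an event that jeopardizes the participant or may require medical or surgical intervention". None of the criteria refers to causality. Section 8.2.2 requires every SAE from consent until 30 days after the end of treatment to be reported regardless of cause.

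**The concern.** The two statements stand next to each other and use different tests. One turns on a causality probability. The other turns on repeat confirmation and on no other cause having been found. Nothing in the section says which prevails.

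The bullet also makes SAE reporting depend on a causality judgement, which the rest of the protocol keeps separate. Section 8.1.1 records the relationship to treatment (item c) and seriousness (item g) as distinct attributes. Section 8.2.2 asks the investigator to assess the relationship of each SAE to each study treatment. There, causality is assessed for an event that is already an SAE; it is not a condition for being one.

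Consistency of reporting is at stake. Two sites with the same liver event could classify it differently, and the SAE tabulations in Section 10.7.1.2 would depend on which sentence each site applied. Section 8.5 provides for no independent data monitoring committee, so sponsor review and SAE reporting carry the safety signal. No efficacy figure or sample size is affected.

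**Working it through.** The protocol has no figure to reproduce here, so the check compares the sets of cases that the two statements cover. All rows assume that the laboratory criteria are met and confirmed on repeat testing.

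| Case | Other cause identified? | Treatment judged >50% likely? | Bullet | Closing paragraph |
|---|---|---|---|---|
| 1 | No | Yes | SAE | SAE |
| 2 | No | No | Not reported as SAE | SAE |
| 3 | Yes, contributing | Yes | SAE | Silent |
| 4 | Yes | No | Not reported as SAE | Silent |

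**Case 1.** The statements agree.

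**Case 2.** The statements contradict each other. The closing paragraph covers all such cases and calls them SAEs. The bullet says that only probable cases should be reported as SAEs, and this case is not probable. It can arise when the work-up is incomplete, or when several other causes are possible but none is established.

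**Case 3.** The statements do not conflict. The closing paragraph gives a sufficient condition for being an SAE and does not say that other cases are not SAEs. The bullet is, however, the only sentence in the section that expressly makes this case reportable, which matters for the fix.

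**Case 4.** The closing paragraph is silent. The event may still be an SAE on another Section 8.2.1 criterion, such as hospitalization. Read literally, the bullet's *only* would exclude it, which does not fit Section 8.2.

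**Against Section 8.2.** The bullet's threshold has no counterpart there. Section 8.2.2 does bring in causality for SAEs arising after the 30-day period, but the test is whether the investigator suspects a relationship, not whether treatment is more likely than all other causes together.

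The closing paragraph is consistent with Sections 8.2.1 and 8.2.2. The bullet is not, because of the scope of one word.

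**The case against.** The strongest reply is that the statements rarely differ in practice. The section itself says "As DILI is essentially a diagnosis of exclusion, other causes of abnormal liver tests should be considered and their role clarified before DILI is assumed". A confirmed case with no other cause found will ordinarily also be judged probable. This stands, and it narrows the problem to case 2, but it does not remove that case.

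A second reply is that the statements can be read in sequence: the bullet governs the label of a DILI case, and the closing paragraph governs what is reported as potential DILI. That is a natural reading and may be what was meant. As written, though, *only such a case* governs both halves of the clause, the label and the SAE reporting, and the protocol nowhere states the distinction.

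A third reply is that Section 8.2 applies independently, so an event that is life-threatening or leads to hospitalization is an SAE whatever Section 6.3.4.2 says. This also stands, and it limits the consequences. It also shows that the bullet's restriction does not fit the general rules.

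A reader might infer three stronger points, and the documents do not support them.

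- *The statements conflict in both directions.* They do not. The closing paragraph is silent on mixed-cause cases and does not exclude them.
- *The bullet delays reporting beyond the limit in Section 8.2.2, "under no circumstances later than within 24 hours of obtaining knowledge of the events".* The wait is not specific to the bullet. The closing paragraph also needs repeat testing and a finding that there is no other cause. Section 8.2.2 does not say when a laboratory finding becomes an SAE.
- *The number of affected cases can be computed.* Assuming that 1% to 5% of about 163 participants (at least 18 in Phase Ib plus about 145 in Phase II) meet the laboratory criteria gives 0.01 × 163 = 1.6 to 0.05 × 163 = 8.2, or about 2 to 8. The rate is an assumption, and the result counts everyone meeting the criteria, not the case 2 subset.

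**Conclusion.** The bullet is wrong as written. It limits SAE reporting to cases judged more than 50% likely to be treatment-caused. The next paragraph and Section 8.2 do not allow that limit.

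The contradiction runs one way and affects one group: confirmed cases with no other cause found that are not judged probable. This group is a subset of the participants meeting the laboratory criteria and is probably small. It could be empty, and the protocol gives no rate from which to size it. Some of its members may be SAEs on other grounds.

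The conclusion rests on the plain wording of the bullet and assumes that no text outside the part of the protocol at hand settles which statement prevails. The correction is worth making because it costs little and the events concerned are ones that Section 6.3.4.2 itself treats as clinically important.

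**What to change.** Reword the end of the bullet so that it decides the label and not the reporting. For example:

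> The label treatment-induced (DILI) is used only where causality is judged probable. SAE status does not depend on this judgement; it follows the paragraph below and Section 8.2. A case with a contributing other cause that is nevertheless judged probably treatment-caused is also reported as an SAE. The causality judgement is recorded in the SAE report or its follow-up.

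Simply deleting the SAE clause would not be enough, because it would remove the only sentence that expressly makes a mixed-cause, probably treatment-caused case reportable. No new timing qualifier is needed in the closing paragraph; adding one would be a separate change to the reporting rules. Section 8.2.2 already provides for follow-up reports, so the later causality judgement has a place to go.

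The cost is about a sentence of wording and possibly a few more SAE reports. The change does not touch any dose, monitoring or discontinuation rule.
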